4.1.2 Exclusion Criteria

Patients who meet any of the following criteria will be excluded from study entry.

Cancer-Specific Exclusions

- Evidence of locally advanced or metastatic bladder cancer (including but not limited to disease involving renal pelvis, ureter, or prostatic urethra)
- Evidence of muscle-invasive bladder cancer
- Evidence of extravesical bladder cancer
- Any malignancy within 5 years prior to Cycle 1, Day 1, except adequately resected basal cell and squamous cell skin cancer or adequately treated carcinoma in situ of the cervix. Patients with malignancies of a negligible risk of metastasis or death (e.g., risk of metastasis or death < 5% at 5 years) may be allowed after discussion with the Medical Monitor.

Patients with prostate cancer who are at low risk and are undergoing active surveillance (Stage T1/T2a, Gleason score ≤ 7 and PSA ≤ 10 ng/mL) are eligible.

- Treatment with any approved anti-cancer therapy, including chemotherapy (systemic or intravesical), radiation therapy (to the bladder or pelvic region), or hormonal therapy within 3 weeks prior to the first dose of study treatment
Use of hormone-replacement therapy and oral contraceptives is permitted.
- Treatment with any other investigational agent or participation in another clinical study with therapeutic intent within 28 days prior to the first dose of study treatment

General Medical Exclusions

- Pregnant or lactating, or intending to become pregnant during the study
Women who are not postmenopausal (≥ 12 months of non-therapy-induced amenorrhea) or surgically sterile must have a negative serum pregnancy test result within 14 days prior to the first dose of study treatment.
- History of severe allergic, anaphylactic, or other hypersensitivity reactions to chimeric or humanized antibodies or fusion proteins
- Known hypersensitivity to biopharmaceuticals produced in Chinese hamster ovary cells
- Allergy or hypersensitivity to components of the atezolizumab formulation
- History of autoimmune disease, including but not limited to myasthenia gravis, myositis, autoimmune hepatitis, systemic lupus erythematosus, rheumatoid arthritis, inflammatory bowel disease, vascular thrombosis associated with anti-phospholipid syndrome, Wegener's granulomatosis, Sjögren's syndrome, Guillain-Barré syndrome, multiple sclerosis, vasculitis, or glomerulonephritis (see [Appendix 6](#) for a more comprehensive list of autoimmune diseases)

Patients with a history of autoimmune-related hypothyroidism on a stable dose of thyroid-replacement hormone may be eligible for this study after discussion with and approval by the Medical Monitor.

Patients with controlled Type 1 diabetes mellitus on a stable insulin regimen may be eligible for this study after discussion with and approval by the Medical Monitor.

- Prior allogeneic stem cell or solid organ transplantation
- History of idiopathic pulmonary fibrosis, organizing pneumonia (e.g., bronchiolitis obliterans), drug-induced pneumonitis, idiopathic pneumonitis, or evidence of active pneumonitis on screening chest CT scan

History of radiation pneumonitis in the radiation field (fibrosis) is permitted.

- Serum albumin <2.5 g/dL
- Positive test for HIV
- Active hepatitis B (defined as having a positive hepatitis B surface antigen [HBsAg] test at screening)

Patients with past or resolved hepatitis B (HBV) infection (defined as having a negative HBsAg test and a positive anti-hepatitis B core antigen [anti-HBc] antibody test) are eligible. HBV DNA must be obtained in these patients prior to the first dose of study treatment.

- Active hepatitis C

Patients positive for hepatitis C virus (HCV) antibody are eligible only if polymerase chain reaction assay is negative for HCV RNA.

- Active tuberculosis
- Severe infections within 28 days prior to the first dose of study treatment, including but not limited to hospitalization for complications of infection, bacteremia, or severe pneumonia
- Signs or symptoms of infection within 14 days prior to the first dose of study treatment
- Treatment with therapeutic oral or IV antibiotics within 14 days prior to the first dose of study treatment

Patients receiving prophylactic antibiotics (e.g., to prevent a urinary tract infection or chronic obstructive pulmonary disease exacerbation) are eligible.

- Significant cardiovascular disease, such as New York Heart Association cardiac disease (Class II or greater), myocardial infarction within the previous 3 months, unstable arrhythmias, or unstable angina
- Major surgical procedure other than for diagnosis within 28 days prior to the first dose of study treatment, or anticipation of need for a major surgical procedure during the course of the study

- Administration of a live/attenuated vaccine within 28 days prior to the first dose of study treatment, within 5 months following the administration of the last dose of study drug, or anticipation that such a live/attenuated vaccine will be required during the study

Influenza vaccination should be given during influenza season only (approximately October to May in the Northern Hemisphere and from April through September in the Southern Hemisphere). Patients must agree not to receive live/attenuated influenza vaccine (e.g., FluMist[®]) within 28 days prior to first dose of study treatment, during treatment or within 5 months following the last dose of atezolizumab.

- Any other diseases, metabolic dysfunction, physical examination finding, or clinical laboratory finding giving reasonable suspicion of a disease or condition that contraindicates the use of an investigational drug or that may affect the interpretation of the results or render the patient at high risk from treatment complications.

Exclusion Criteria Related to BCG

- History of prior significant toxicity or intolerance to BCG requiring discontinuation of treatment
- History of prior systemic BCG infection

Note: This is applicable to patients receiving combination BCG and atezolizumab therapy (Cohorts 1B or 2). Patients in Cohort 1A may be eligible, pending that they have received an adequate course of BCG and meet all other eligibility criteria.

- History of immunosuppression, or conditions associated with congenital or acquired immune deficiency, whether because of concurrent disease (e.g., AIDS, leukemia, lymphoma), cancer therapy (e.g., cytotoxic drugs, radiation), or immunosuppressive therapy (e.g., corticosteroids)
- Concurrent febrile illness, urinary tract infection, or gross hematuria

Exclusion Criteria Related to Medications

- Prior treatment with CD137 agonists or immune checkpoint blockade therapies, including anti-cytotoxic T lymphocyte-associated antigen 4, anti-PD-1, and anti-PD-L1 therapeutic antibodies
- Treatment with systemic immunostimulatory agents (including but not limited to IFNs and IL-2) within 6 weeks or five half-lives of the drug, whichever is shorter, prior to the first dose of study treatment

- Treatment with systemic immunosuppressive medications (including but not limited to prednisone, cyclophosphamide, azathioprine, methotrexate, thalidomide, and anti-TNF- α agents) within 2 weeks prior to the first dose of study treatment, or anticipated requirement for systemic immunosuppressive medications during the study.

Patients who have received acute, low-dose, systemic immunosuppressant medications (e.g., a one-time dose of dexamethasone for nausea) may be enrolled in the study after discussion with and approval by the Medical Monitor.

The use of inhaled corticosteroids and mineralocorticoids (e.g., fludrocortisone) is allowed. Use of physiologic doses of corticosteroids for adrenal insufficiency is allowed.

4.2 METHOD OF TREATMENT ASSIGNMENT AND BLINDING

This is an open-label study. The investigator will determine the appropriate cohort for each patient.

4.3 STUDY TREATMENT

4.3.1 Formulation, Packaging, and Handling

4.3.1.1 Atezolizumab

Atezolizumab will be supplied by the Sponsor as sterile liquid in 20-mL glass vials. The vial is designed to deliver 20 mL (1200 mg) of atezolizumab solution but may contain more than the stated volume to enable delivery of the entire 20 mL volume. For information on the formulation and handling of atezolizumab, refer to the Investigator's Brochure and Pharmacy Manual.

4.3.1.2 Bacille Calmette-Guérin

OncoTICE[®] BCG for intravesical use is an attenuated, live culture preparation of the BCG strain of *Mycobacterium bovis*. The freeze-dried BCG preparation is delivered in glass vials, each containing 1 to 8×10^8 CFU of OncoTICE BCG, which is equivalent to approximately 50 mg wet weight. No preservatives have been added.

A single dose consists of one reconstituted vial. For intravesical use, the entire vial is reconstituted with sterile saline. OncoTICE BCG is viable upon reconstitution.

Patients should minimize fluid intake before treatment with BCG. Additionally, complete bladder drainage should occur via catheter drainage placed immediately prior to BCG administration.

In the event of a supply shortage of OncoTICE BCG, sites may be allowed to use a local stock of BCG on a case-by-case basis after approval by the Sponsor.

For detailed information on the formulation and handling of BCG, see the local OncoTICE prescribing information.

The following summarizes AUA voiding instructions and other precautions to patients following BCG exposure:

Precautions post procedure: after the first void and for the next 6 hours include:

- a) Sit to void to avoid urine splashing. Do not use public toilets or void outside.
- b) After each void, add 2 cups undiluted bleach to toilet, close the lid, and wait 15–20 minutes, and then flush the toilet. Repeat with each void for 6 hours.
- c) Increase fluid intake to dilute the urine. Begin after the first void post procedure.
- d) Common side effects within 24 hours post procedure: blood in urine; low-grade fever (99–100 °F); tiredness; urinary frequency, urgency, and burning with urination; and muscle or joint achiness. You will be given prescriptions to address the urinary symptoms (frequency, urgency, and burning on urination) if needed.
- e) If sexually active, wear a condom with intercourse throughout the entire treatment course and for six weeks after treatment has ended.
- f) Urinary incontinence: Immediately wash clothes in clothes washer. Do not wash with other clothes.
- g) If wearing incontinence pad, pour bleach on pad, allow to soak in, then place in plastic bag, and discard in trash.
- h) Call urology clinic or provider if patient develops fever more than 101.3 °F (38.5 °C), chills, or rigors.
- i) May use acetaminophen or ibuprofen for fever and body aches.
- j) May need antispasmodic medication to help with frequency and urgency.

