There may be circumstances in which either BCG or atezolizumab is permanently discontinued, but it may still be possible to continue the remaining study treatment with approval of the Medical Monitor. Patients in Cohorts 1B, 2, or 3 (atezolizumab plus BCG) who discontinue atezolizumab after receiving fewer than three cycles may be replaced.

All patients will be closely monitored for serious adverse events or protocol-defined events of special interest for 90 days or 30 days for adverse events, following their last dose of study therapy (atezolizumab and/or BCG) or initiation of non-protocol anti-cancer therapy, whichever occurs first. Safety assessments will include the incidence, nature, and severity of adverse events, changes in selected vital signs and laboratory abnormalities graded per NCI CTCAE v4.0.

Serum and plasma samples will be collected to monitor atezolizumab pharmacokinetics and to detect the presence of antibodies to atezolizumab.

Patient samples, including archival tumor tissues, as well as plasma, whole blood, and urine will be collected for future exploratory biomarker assessments.

A treatment completion/discontinuation visit will be performed for all patients within 30 days after the last administration of study treatment.

[figure not shown]
Patients who discontinue study treatment for a reason other than disease recurrence/progression or cystectomy (e.g., because of toxicity) will continue to undergo tumor assessments per protocol until they experience disease recurrence/progression or cystectomy, until the patient dies, withdraws consent, or until the study closes, whichever occurs first, for a maximum of 5 years after enrollment.

In addition, all patients will be followed for survival and subsequent anti-cancer therapy beginning 6 months after the treatment completion/discontinuation until loss to follow-up, death, withdrawal of consent, or study termination by the Sponsor, whichever occurs first, for a maximum of 5 years after enrollment.

Figure 6 presents the treatment plans for each cohort. The schedules of assessments are provided in Appendix 1 and Appendix 2.

[figure not shown]
Figure 6 Treatment Plans

Cohort 1A

Cohort 1A: Patients receive atezolizumab 1200 mg IV q3w.

Cohort 1B

[figure not shown]

BCG = bacille Calmette-Guérin.

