The initial dose of atezolizumab will be delivered over 60 (\pm 15) minutes. If the first infusion is tolerated without infusion-associated adverse events, the second infusion may be delivered over 30 (\pm 10) minutes. If the 30-minute infusion is well tolerated, all subsequent infusions may be delivered over 30 (\pm 10) minutes. For the first infusion, the patient's vital signs (heart rate, respiratory rate, blood pressure, and temperature) should be determined within 60 minutes before, during (every 15 [\pm 5] minutes), and 30 (\pm 10) minutes after the infusion. For subsequent infusions, vital signs will be collected within 60 minutes before infusion and at the end of the infusion. Patients will be informed about the possibility of delayed post-infusion symptoms and instructed to contact their study physician if they develop such symptoms.

No premedication is indicated for the administration of atezolizumab in Cycle 1. Patients who experience an infusion-related reaction with Cycle 1 of atezolizumab may receive premedication with antihistamines or antipyretics/analgesics (e.g., acetaminophen) for subsequent infusions (see [Table 7](#)).

Table 7 Guidelines for the Management of Infusion-Related Reactions during the First Atezolizumab Infusion

Toxicity	Severity	Management
Infusion-related reaction	Grade 1	
 • Reduce infusion rate to half the rate being given at the time of event onset. • After the event has resolved, the investigator should wait for 30 minutes while delivering the infusion at the reduced rate. • If tolerated, the infusion rate may then be increased to the original rate.
	Grade 2	
 • Interrupt atezolizumab infusion. • Administer aggressive symptomatic treatment. • Restart only after the symptoms have adequately resolved to baseline grade. • The infusion rate at restart should be half of the infusion rate that was in progress at the time of the onset of the IRR. • At next cycle, administer oral premedication with antihistamine and anti-pyretic and monitor closely for infusion reaction.
	Grade 3 or 4	
 • Stop infusion. • Proper medical management which may include oral or IV antihistamine, anti-pyretic, glucocorticoids, epinephrine, bronchodilators, and oxygen. • Discontinue atezolizumab. • Contact the Medical Monitor if atezolizumab is discontinued.

For anaphylaxis precautions, see [Appendix 8](#).

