4.5 STUDY ASSESSMENTS

EAU and NCCN guidelines recommend surveillance monitoring for high-risk NMIBC with cystoscopy and urine cytology every 3–6 months for the first 2 years, which is consistent with the tumor assessment schedule for this study (Babjuk et al. 2011; NCCN 2014).

See [Appendix 1](#) and [Appendix 2](#) for the schedules of assessments performed during the study.

Patients will be closely monitored for safety and tolerability throughout the study. All assessments must be performed and documented for each patient.

Patients should be assessed for toxicity prior to each dose of atezolizumab and BCG; dosing will occur only if the clinical assessment and local laboratory test values are acceptable.

If the timing of a protocol-mandated study visit coincides with a holiday and/or weekend that precludes the visit, the visit should be scheduled on the nearest following feasible date, with subsequent visits scheduled according to the original schedule.

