5.1.2.1 Constitutional Symptoms (Flu-like Symptoms)

Flu-like symptoms (malaise, fever and chills) may occur with both BCG treatment and atezolizumab. In patients who develop flu-like symptoms, disseminated BCG infection should be evaluated and ruled out before attributing to atezolizumab. The management of disseminated BCG infection requires the administration of antibiotics and steroids would be contraindicated. Patients should be monitored for the presence of symptoms and signs of toxicity after each intravesical treatment. Flu-like symptom attributable to BCG may be managed per the OncoTICE prescribing information.

Additional guidelines for management of patients who develop flu-like symptoms are provided in [Table 8](#).

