Grade 3/4	
 Withhold atezolizumab. Consider starting 10 mg/day oral prednisone or equivalent, with taper over 1–2 weeks. Resume atezolizumab if symptoms resolve and corticosteroid dose is equivalent to 10 mg/day. Refer to the TICE prescribing information for additional management guidelines pertaining to BCG.
Fever	
< 101° F (38.3° C)	
 Continue atezolizumab and BCG (patients receiving induction or maintenance BCG at time of symptom) Treat symptoms with non-steroidal anti-inflammatory drugs (e.g., ibuprofen). Withhold BCG and atezolizumab.
$\geq 101^{\circ}$ F (38.3° C)	
 For fever < 24 hours, and in absence of other new grade ≥ 2 symptoms, evaluate and rule out co-existing infection including urine and blood culture, blood tests, and chest X-ray. Consider consultation with infectious disease specialist. For fever > 24hours, would recommend immediate consultation with infectious disease specialist, discontinuation of BCG instillations, urine and blood culture, blood tests, and chest X-ray. Consider initiation of ≥ 2 antimicrobial agents including coverage with anti-tuberculosis therapy while diagnostic evaluation is being conducted. Refer to the TICE prescribing information for additional management guidelines pertaining to BCG.
Local bladder symptoms	
Dysuria	
 Refer to the TICE prescribing information for management guidelines pertaining to BCG.
Frequency	
 Refer to the TICE prescribing information for management guidelines pertaining to BCG.
Hematuria	
 Refer to the TICE prescribing information for management guidelines pertaining to BCG.
Local inflammation (e.g., epididymitis, prostatitis, orchitis)	
 Refer to the TICE prescribing information for management guidelines pertaining to BCG.

BCG = bacille Calmette-Guérin; GGO = ground-glass opacity; IV = intravenous; LFT = liver function test; TNF- α = tumor necrosis factor- α ; TSH = thyroid-stimulating hormone; ULN = upper limit of normal.

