Atezolizumab Cycle # (Day 1) ^{a,b}	1			2			3			4			5			6			7			8			9			10			11	
BCG Administration ^{b,c}	x	x	x	x	x	x							x	x	x										x	x	x					
Cystoscopy/ Cytology ^d											x													x								
Upper Tract Imaging ^{b,e}																										x						

Week on Study	31	32	33	34	35	36	37	38	39	40	41	42	43	44	45	46	47	48	49	50	51	52	53	54	55	56	57	58	59	60	
Study Month																							12								
Atezolizumab Cycle # (Day 1) ^{a,b}			12			13			14			15			16			17			18			19			20			21	
BCG Administration ^{b,c}																		x	x	x											
Cystoscopy/ Cytology ^d						x										x														x	
Upper Tract Imaging ^{b,e}																															

Appendix 3
BCG and Atezolizumab Treatment and Tumor Assessment Calendar for Study Weeks 0–108:
Cohorts 1B, 2 and 3 (cont.)

Week on Study	61	62	63	64	65	66	67	68	69	70	71	72	73	74	75	76	77	78	79	80	81	82	83	84	85	86	87	88	89	90
Study Month																		18												
Atezolizumab Cycle # (Day 1) ^{a,b}			22			23			24			25			26			27			28			29			30			31
BCG Administration ^{b,c}												x	x	x																
Cystoscopy/ Cytology ^d										x														x						
Upper Tract Imaging ^{b,e}																								x						

Week on Study	91	92	93	94	95	96	97	98	99	100	101	102	103	104	105	106	107	108 ^f
Study Month														24				
Atezolizumab Cycle # (Day 1) ^{a,b}			32															
BCG Administration ^{b,c}						x	x	x										
Cystoscopy/ Cytology ^d				x														x
Upper Tract Imaging ^{b,e}																		

Appendix 3

BCG and Atezolizumab Treatment and Tumor Assessment Calendar for Study Weeks 0–108: Cohorts 1B, 2 and 3 (cont.)

- ^a Atezolizumab will be administered by IV infusion. During BCG Induction Course (12 weeks), patients receive atezolizumab 1200 mg IV q3w for a total of four doses. During BCG Maintenance Course 1 (12 weeks), patients will receive atezolizumab 1200 mg IV q3w for a total of four doses. During BCG Maintenance Course 2–5 (each 24 weeks), patients receive atezolizumab 1200 mg IV q3w for a total of eight doses per course. The maximum treatment duration is 96 weeks or 32 cycles, whichever occurs first.
- ^b All visits must occur within ± 3 days from the scheduled date unless otherwise noted.

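### After BCG, patients are told to call for fever above 101.3 °F (38.5 °C), but Table 8 acts from 101 °F (38.3 °C), so an isolated home fever of 101.0–101.3 °F prompts no call under Section 4.3.1.2 item h

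*Combined protocol and SAP*

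**What the plan says.** Section 4.3.1.2 lists precautions for patients after a BCG instillation. Item h gives the call rule: "Call urology clinic or provider if patient develops fever more than 101.3 °F (38.5 °C), chills, or rigors". Item i follows with "May use acetaminophen or ibuprofen for fever and body aches" and sets no upper temperature. Item d describes the common low-grade fever as 99–100 °F and attaches no action to it.

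The fever rows of Table 8 in Section 5.1.3 (not the pancreatic Table 8 of Appendix 12) divide at 101 °F (38.3 °C). Below that, both drugs continue and symptoms are treated. At or above it, both drugs are withheld. For a fever of under 24 hours without other new grade 2 or worse symptoms, infection is to be ruled out with cultures, blood tests and chest X-ray. For longer fever the table states: "For fever > 24hours, would recommend immediate consultation with infectious disease specialist, discontinuation of BCG instillations".

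Three other provisions bear on whether the site would hear of such a fever:

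- Sections 4.3.2.1 and 4.5.4, on atezolizumab infusions: "Patients will be informed about the possibility of delayed post-infusion symptoms and instructed to contact their study physician if they develop such symptoms".
- Section 5.1.2.1, on flu-like symptoms: "Patients should be monitored for the presence of symptoms and signs of toxicity after each intravesical treatment".
- Section 4.5: "Patients should be assessed for toxicity prior to each dose of atezolizumab and BCG".

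**The concern.** A clinician can apply Table 8 to a fever at home only after learning of it. The patient's call level should therefore be no higher than the level at which the clinician is expected to act. Here it is higher, and the protocol does not explain the difference. In the band between the two levels, item h asks for no call and item i allows an antipyretic.

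Fever matters in this setting. BCG is a live culture. Section 5.1.2.1 wants disseminated BCG infection ruled out before flu-like symptoms are attributed to atezolizumab, and treats steroids as contraindicated if that infection is present. BCG infection is also an adverse event of special interest (Section 5.2.3). What is at stake is the start of the Table 8 work-up, and of the consultation when the fever passes 24 hours.

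**Working it through.** **1. The printed temperatures.** With °F = °C × 9/5 + 32, 38.5 °C gives 101.30 °F, and 38.3 °C gives 100.94 °F, which rounds to 101 °F. Both printed pairs are consistent, so the difference between the two rules is not a conversion slip. In the other direction, (101 − 32) × 5/9 = 38.33 °C and (101.3 − 32) × 5/9 = 38.50 °C. The band is 0.3 °F, or 0.17 °C, wide.

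**2. The two rules applied to an isolated fever without chills or rigors.**

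| Temperature (°F) | Item h (> 101.3): call? | Table 8 (≥ 101): withhold and evaluate? |
|---|---|---|
| 100.9 | no | no |
| 101.0 | no | yes |
| 101.1 | no | yes |
| 101.2 | no | yes |
| 101.3 | no | yes |
| 101.4 | yes | yes |

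In the extracted text the instruction to withhold both drugs is printed just ahead of the ≥ 101 °F label. It must belong to that row, because the row below 101 °F says to continue both drugs. The infection work-up is in the upper row in any case.

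**3. How far the post-infusion instruction reaches.** Inputs are from the Appendix 3 calendar.

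- BCG weeks: 0–5, 12–14, 24–26, 48–50, 72–74 and 96–98, so 6 + 5 × 3 = 21 instillations. Of these, 6 + 3 = 9 precede the 6-month assessment.
- Atezolizumab weeks: 0, 3, …, 93, so 32 doses.
- Both due in the same week: Weeks 0, 3, 12, 24, 48 and 72, so 6 of 21.
- BCG 0–2 weeks after an infusion: Weeks 0–2, 3–5, 12–14, 24–26, 48–50 and 72–74, so 6 × 3 = 18 of 21. Before the 6-month assessment it is 9 of 9.
- The other three, Weeks 96–98, fall 3–5 weeks after the last infusion at Week 93.

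This is the full calendar. Cohort 1A receives no BCG, and Maintenance Courses 2–5 are optional in Cohort 1B.

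**4. When the pre-dose check comes.** After every BCG week except Week 98 (20 of 21), a dose of one drug or the other is due one week later. Appendix 3 footnote b, like Section 4.5.9, says: "All visits must occur within ± 3 days from the scheduled date unless otherwise noted". With that window at both visits, the interval runs from 7 − 6 = 1 day to 7 + 6 = 13 days. After Week 98 no dosing visit follows; Section 3.1.2 says: "A treatment completion/discontinuation visit will be performed for all patients within 30 days after the last administration of study treatment".

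**5. What each provision covers.** The post-infusion instruction gives neither a temperature nor a duration, and is tied to atezolizumab. The monitoring sentence in Section 5.1.2.1 gives no method and no call level. Item d puts 101 °F above what patients are told to expect, without telling them what to do. The pre-dose check largely protects the next dose, but at a nominal 7 days it does not deliver a work-up in the first 24 hours or an immediate consultation after that.

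**The case against.** The strongest reply is that the two figures have different purposes. The list in Section 4.3.1.2 summarizes urological-association advice to patients, whereas Table 8 guides clinicians once a fever is known. Item h says when to call and does not forbid calling sooner. A patient told to expect 99–100 °F may well call at 101 °F. The exposed case is also narrow: the fever must reach 101.0 °F, never pass 101.3 °F, and come without chills or rigors. For the consultation step it must also last more than 24 hours. All of this stands and limits the weight of the point. It does not remove the mismatch, because Table 8 depends on the site being told.

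A reader might infer from the 6 same-week dosings that patients have no contact route after the other 15 of 21 instillations. The documents do not support that. The instruction concerns delayed symptoms and has no stated time limit, 18 of 21 instillations fall 0–2 weeks after an infusion, and a patient on both drugs cannot tell which one caused a fever. Nor can 18 of 21 be taken as proven coverage, since the protocol does not say how long delayed symptoms may take to appear.

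A reader might also infer that patients in the trial were never given a 101 °F call level. That cannot be known here: the consent pages were removed and the BCG prescribing information is not available.

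**Conclusion.** The mismatch is real and minor. Under the protocol text, an isolated home fever of 101.0–101.3 °F (38.33–38.50 °C) after BCG meets the Table 8 action level without prompting a call under item h. The post-infusion instruction is a partial backstop, and the pre-dose check largely protects the next dose. What remains is a possible delay in work-up or consultation, for a band of fevers whose frequency the documents do not give.

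The conclusion assumes that the Appendix 3 calendar is followed and that no unseen patient material sets a lower call level. The comparison of the two cut-offs is certain; the size of any safety effect is not. It would be wrong to read more into it: no endpoint, DLT rule, estimate or sample size depends on the item h call level.

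**What to change.** Change item h of Section 4.3.1.2 so that patients call for fever of 101 °F (38.3 °C) or higher, chills, or rigors, and make any patient instructions match. Every temperature in the upper fever row of Table 8 would then also prompt a call, and the band disappears.

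The cost is one changed number, a few more phone calls and routine amendment handling. Section 9.7 requires ethics approval of protocol changes. If consent forms repeat the present level, Section 8.2 calls for revised forms and re-consent. The change can go with any other amendment. No statistical quantity has to be recalculated.
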